## LIST OF ABBREVIATIONS AND DEFINITION OF TERMS

Abbreviation	Definition
AE(s)	Adverse Event(s)
B&A	Balance and Assignment
CDA	Confidentiality Disclosure Agreement
CFR	Code of Federal Regulations
CRF(s)	Case Report Form(s)
DMI	Dry Mouth Inventory Questionnaire
ECRF	Electronic Case Report Form(s)
FDA	Food and Drug Administration
GCP	Good Clinical Practices
IRB/IEC	Institutional Review Board/Independent Ethics Committee
MD	Moisturization and Dryness Questionnaire
PPAQ I	Product Performance and Attributes Questionnaire I
PPAQ II	Product Performance and Attributes Questionnaire II
SOP(s)	Standard Operating Procedure(s)

## PROTOCOL BODY

### 1. Background

Xerostomia or dry mouth is a subjective sensation of oral dryness. It affects 5.5 to 46% of the adult population with higher prevalence in females and older people (however this condition is not related to age itself). The degree of xerostomia and salivary hypofunction do not always correlate with each other. Xerostomia may be caused by a variety of underlying etiologies, including systemic diseases (diabetes, cardiac disease, cancer and cancer treatments, rheumatoid arthritis, Alzheimer's disease, Parkinson's disease, HIV/AIDS, Sjögren's Syndrome, anemia), medications, head and neck radiation and modifiable lifestyle factors (smoking, sleep apnea, alcohol use etc.). Treatment of clinical symptoms of xerostomia can be divided into two categories: systemic sialagogues (pilocarpine and cevimeline) and topic agents like saliva substitutes, topical lubrication products, candies, chewing gum and water.

*Ref: Etiology, evaluation, and management of xerostomia Jillian W. Millsop, Elizabeth A. Wang, Nasim Fazel. Clinics in Dermatology. Volume 35, Issue 5, September–October 2017, Pages 468-476*

### 2. Study Objective

The objective of this study is to evaluate dry mouth relief in subjects with self-reported feeling of dry mouth after using an experimental mouth rinse or a positive control compared to a water control.

### 3. Overall Study Design and Plan

This is a randomized, 3-treatment, parallel study for subjects with self-reported dry mouth symptoms as determined by an Oral Examination and subject responses to the Dry Mouth Inventory (DMI) questionnaire (see section 12) at the Acclimation visit. Qualified subjects will be randomly assigned to one of three treatments at the Baseline visit. Safety will be assessed by Oral Examinations at Baseline/Day1 and Day 8. Subjects will complete questionnaires before product use, immediately after product use, and after 30 minutes, 1 hour, 2 hours, 4 hours and 6 hours of product use on Baseline/Day 1 and Day 8. The PPAQ II questionnaire will be completed on the morning of Day 8 (see study schedule for details).

**Table 1. Study Schedule by Procedure Type and Visit**

Procedures	Acclimation Visit 1	Baseline/ Day 1 Visit 2	Day 8 Visit 3
Informed Consent	X		
CDA	X		
Medical History	X		
Demographics	X		
DMI Questionnaire	X		
Inclusion/Exclusion	X		
Acclimation Product Distribution	X		
Continuance Criteria		X	X
Baseline MD Questionnaire		X	
Oral Examination	X	X	X
Treatment Randomization		X	
Treatment Product Distribution		X	
Product Use		X	X
Immediate MD Questionnaire		X	
PPAQ I/ MD Questionnaire- 30 minutes		X	X**

PPAQ I/ MD Questionnaire- 1 hour		X	X**
PPAQ I/ MD Questionnaire- 2 hour		X	X**
PPAQ I/ MD Questionnaire- 4 hour		X	X**
PPAQ I/ MD Questionnaire- 6 hour		X	X**
PPAQ II Questionnaire			X*
Product Diary Distribution		X	
Product Diary Return			X
Treatment Product Return			X
General Comments	X	X	X
AEs		X	X
Subject Accountability			X

\* PPAQ II will be completed at home immediately after waking up. \*\* No MD Questionnaire will be asked on Day 8

All questionnaires (except for PPAQ II) will be conducted over the phone by site staff. Subjects will have paper copies of the questionnaires as a reference. Site staff will directly enter the subject responses into the study database. Before asking the questions, site staff will ensure that all study procedures were followed (i.e. no eating or drinking). Product diaries will be completed on paper and reviewed outside the study database.

#### Acclimation (Visit 1)

At the site, subjects will be asked to read and sign an informed consent form and Confidentiality Disclosure Agreement (CDA) and will receive a signed copy for their records. Personal medical history information will be reviewed and retained as site source documentation. Demographic information will be recorded, and subjects will answer the DMI questionnaire to ensure study eligibility. An Oral Examination will be performed. Entrance criteria will be assessed. Up to 150 qualifying subjects will receive acclimation toothbrush, toothpaste, and usage instructions. Subjects will begin using these acclimation products in place of their normal oral hygiene products for the duration of the study. They will be instructed to brush their teeth in the morning of Baseline/Day 1 and Day 8 study visits.

#### Baseline/Day 1 (Visit 2)

Continuance criteria will be assessed. Subjects will have an Oral Examination at the site. Subjects will be randomly assigned to one of three treatment groups by a Balance & Assignment (B&A) program based on age and DMI severity score. Assigned treatment product kit boxes will be distributed and written instructions reviewed. In addition, all groups will be instructed to continue using the acclimation products per acclimation instructions. Subjects will be sent home with copies of questionnaires, their assigned kit box, the product diary, and the standardized snack. While at home, subjects will complete the Baseline MD questionnaire over the phone with site staff. Subjects will then use their assigned product for the first time and then a timer will be set for 6 hours. Immediately following the product use, subjects will complete the Immediate MD Questionnaire over the phone with site staff. Site staff will contact the subjects at home at the corresponding timepoints for completing the remaining questionnaires, (the PPAQ I/ MD 30-minute Questionnaire, the PPAQ I/ MD 1-hour, 2-hour, 4-hour and 6-hour Questionnaires).

Subjects will be instructed to refrain from eating, drinking, smoking, using their test products, using tobacco, using a medicated lozenge, chewing gum, or breath mints during the 6-hour test period. Subjects may consume their provided standardized snack immediately after the 4-hour questionnaire.

Should a subject not be able to follow the drinking or eating restrictions for the full six hours (i.e. require a rescue product such as water), the subject will be asked to fill out the next set of questionnaires, and then they will be allowed to resume normal activity for the rest of Day 1. Site staff will record the time the subject completed the questionnaires in General Comments. If desired, the subject will be allowed to remain in the study.

After the 6-hour questionnaire, subjects will be reminded to adhere to their assigned product use instruction sheet for the duration of the study. Subjects will be asked to complete the product diary tracking their product usage and water intake. Subjects from all groups will be allowed to sip water as needed on Days 2 – 7. Subjects will be reminded to bring their acclimation and treatment kit boxes and completed product diary to their next study visit.

#### Day 8 (Visit 3)

The night before this study visit, subjects will be reminded to complete the PPAQ II Questionnaire immediately after waking up in the morning (before eating, drinking, brushing their teeth, chewing gum or smoking). Subjects will also be reminded to adhere to their assigned treatment instruction sheet prior to coming to the site.

At the site, continuance criteria will be assessed. The completed PPAQ II will be collected and subsequently transcribed into the database by site staff (acclimation kit boxes may be collected at this visit). An Oral Examination will be performed. After the oral exam, subjects will be sent home with copies of questionnaires, their assigned kit box, the product diary, and the standardized snack. While at home, subjects will use their assigned product and notify site staff, and then a timer will be set for 6 hours. Subjects will complete the PPAQ I 30-minute Questionnaire, the PPAQ I 1-hour, 2-hour, 4-hour and 6-hour Questionnaires over the phone with site staff.

Subjects will be instructed to refrain from eating, drinking, smoking, using their test products, using tobacco, using a medicated lozenge, chewing gum, or breath mints for the during the 6-hour test period. Subjects may consume the provided standardized snack immediately after the 4-hour questionnaire. After completing the 6-hour questionnaires, the subject will be given instructions from site on how to return study products and product diary. The subject will then be dismissed from the study, and a Subject Accountability form will be completed.

Should a subject not be able to follow the drinking or eating restrictions for the full six hours (i.e. require a rescue product such as water), the subject will be asked to fill out the next set of questionnaires. Site staff will record the time the subject completed the questionnaires in General Comments. The subject will then be dismissed from the study.

#### Subject Accountability

If, for any reason, a subject does not complete the study, an explanation will be entered on the Subject Accountability eCRF. All data gathered on the subject prior to discontinuation will be made available to the Sponsor.

#### General Comments and Adverse Events

General comments can be recorded at any time during the study. Any AE will be documented in ECRF. Any self-reported AE that remains unresolved by the end of the study should be followed up until resolution by the investigator/designee, and the resolution should be documented only as source documentation. If a subject is unreachable to determine whether the AE has been resolved, the attempts to contact the subject should be documented as source documentation. Examiner observed AEs that are unresolved at the end of the study are followed to resolution at the discretion of the Medical Monitor.

## **4. Inclusion Criteria**

In order to be included in the study, each subject must:

- Provide written informed consent prior to participation and be given a signed copy of the informed consent form;
- Sign a Confidentiality Disclosure Agreement (CDA) form and be given a signed copy;
- Be at least 18 years of age;
- Agree not to participate in any other oral care studies for the duration of this study;

- Agree to delay elective dentistry, including dental prophylaxis, until study completion, and to report any non-study dentistry received during the course of the study;
- Agree to refrain from the use of any non-study oral hygiene products for the study duration including mouth rinse and toothpaste (flossing is permitted if part of their normal routine);
- Self-report a dry mouth feeling according to the modified DMI questions (Subject must answer at least 2 out of 4 questions with 'agree a little,' 'agree' or 'strongly agree');
- Agree to refrain from eating, drinking, smoking, using oral care products, using tobacco, using a medicated lozenge, chewing gum, or breath mints during the 6-hour test period (except snack after 4-hour Questionnaire);
- Agree to return for all scheduled visits and to follow all study procedures.

## 5. Exclusion Criteria

Subjects will be excluded from study participation where there is evidence of:

- Any condition or disease, as determined by the Investigator/Designee, that could be expected to interfere with examination procedures, with compliance, or with the subject's safe completion of the study;
- Severe periodontal disease, as characterized by purulent exudate, generalized mobility, and/or severe recession;
- Active treatment for periodontitis;
- Having a history of allergies or hypersensitivity to mouth rinse or ingredients in commercial dental products or cosmetics;
- Self-reported pregnancy or the intent to become pregnant during the study, or breast feeding;
- Full or partial dentures or any orthodontic appliances such as braces or aligners, or tongue or mouth piercing;
- Inability to undergo any study procedure;
- Having untreated oral mucosal disease which in the opinion of the investigator could interfere with the study (e.g., current oral ulceration); or
- Evidence of gross intra-oral neglect or need for extensive dental therapy.

## 6. Continuance Criteria

Subjects may be excluded from the study or the analysis if they:

- Have participated in any other oral care study since the last study visit;
- Since the last study visit, have developed any condition or disease or taken a new medication, which as determined by the Investigator/Designee could be expected to interfere with examination procedures, with compliance, or with the subject's safe completion of the study;
- Used any non-study oral hygiene products since the last study visit;
- Used study mouth rinse prior to the study visit (*Day 8 only*); or
- Had any non-study dentistry, including dental prophylaxis, performed since the last study visit.

## 7. Identity of Investigational Product(s)

- Acclimation/Washout: Burt's Bees Enamel Care Toothpaste (0.243% sodium fluoride, 0.13% w/v fluoride ion) and an Oral-B Indicator toothbrush
- Experimental Rinse Group: Burt's Bees Enamel Care Toothpaste (0.243% sodium fluoride, 0.13% w/v fluoride ion), Experimental mouth rinse (0.1% Sodium Hyaluronate), and an Oral-B Indicator toothbrush
- Positive Control Group: Burt's Bees Enamel Care Toothpaste (0.243% sodium fluoride, 0.13% w/v fluoride ion), GUM® Hydral Dry Mouth Relief daily oral rinse, and an Oral-B Indicator toothbrush
- Water Control Group: Burt's Bees Enamel Care Toothpaste (0.243% sodium fluoride, 0.13% w/v fluoride ion), 15ml of water and an Oral-B Indicator toothbrush

## 8. Product Usage

### At-home brushing

Subjects will brush their teeth thoroughly, twice daily (morning and evening) as they normally do with the provided toothpaste and toothbrush. Subjects will be asked to use this toothpaste and toothbrush for the duration of the study, for both the acclimation and treatment period. Flossing and tongue brushing are permitted during the study if it is part of their normal routine.

### Experimental Rinse Group

Day 1 and Day 8 first use: Subjects will rinse with 15ml of mouth rinse for 30 seconds. Subjects will record usage in their product diary. Subjects will not be allowed to use any mouth rinse during the 6-hour time period on Baseline/Day 1 and Day 8.

After first use Day 1- Day 7: Subjects will be instructed to use the rinse product (15ml for 30 seconds) at least twice a day, up to 5 times a day. The rinse can be used alone or after each brushing. Subjects will record all usage in their product diary.

### Positive Control Group

Day 1 and Day 8 first use: Subjects will rinse with 15ml of mouth rinse for 30 seconds. Subjects will record usage in their product diary. Subjects will not be allowed to use any mouth rinse during the 6-hour time period on Baseline/Day 1 and Day 8.

After first use Day 1 – Day 7: Subjects will be instructed to use the rinse product (15ml for 30 seconds) at least twice a day, up to 5 times a day. The rinse can be used alone or after each brushing. Subjects will record all usage in their product diary.

### Water Control Group

Day 1 and Day 8 first use: Subjects will rinse with 15ml of water for 30 seconds. Subjects will record usage in their product diary. Subjects will not be allowed to use any water rinse during the 6-hour time period on Baseline/Day 1 and Day 8.

After first use Day 1 – Day 7: Subjects will be instructed to rinse with water (15ml for 30 seconds) at least twice a day, up to 5 times a day. The rinsing can be used alone or after each brushing. Subjects will record all usage in their product diary.

Subjects from all groups will be allowed to sip water as needed on Days 2 – 7, water intake should be captured in their product diaries.

## 9. Blinding, Labeling, and Shipping Plan

Acclimation take-home kit boxes will be labeled with study number, emergency phone number, distributor name/address, appropriate caution statements, content statement and other information as required by internal regulations and clinical SOPs. Treatment take-home kit boxes will be identically sized and labeled with a unique kit box number or code, study number, emergency phone number, distributor name/address, appropriate caution statements, content statement and other information as required by internal regulations and clinical SOPs. The shipping containers will be labeled with the clinical site address and a content statement listing study number and kit box numbers contained within. The site will be provided with supplemental product.

The site will be provided with a code breaker report in a sealed envelope. The sealed code breaker report contains documents that list the kit box number or treatment code while the identity of the treatment products is hidden by an opaque scratch-off seal. If the study blind needs to be broken, an individual subject's investigational product may be ascertained by opening the sealed code breaker report, locating the subject's kit box number or treatment code and scratching off the opaque seal to reveal the treatment identity. The sealed code breaker report will be opened if a clinically serious AE

occurs or management of the subject requires knowledge of the identity of the investigational product. The Investigator should immediately inform the Sponsor that the code will be broken and record the date, time and reason for breaking the code in writing. After the study is complete and the study database has been finalized and locked, the site will return the code breaker report to the Sponsor.

## 10. Method of Assigning Subjects to Treatment Groups

Study Design	n	n/group	B&A Program	PRA Block Size	Strata	Cut-offs*	Cohab
Parallel	150	50	Yes	3	DMI Severity Score; Age	Mild (2-5), Moderate (6-8), Severe (9-12); <=54, >54	Yes

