### B&A Program

At the Baseline visit, subjects will be randomly assigned to one of the three treatment groups (up to 50 per group) using an encoded B&A program supplied by the Sponsor. The subjects will be stratified based on DMI Severity Score and age. Subjects residing in the same household will be assigned to the same treatment group.

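### A fixed, printed block size of 3 may make water-or-rinse assignment partly predictable at the site; randomly varying, undisclosed blocks would reduce this at almost no cost

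*Combined protocol and SAP*

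**What the plan says.** All places are in the combined protocol and SAP.

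- **Block size.** The table in section 10 gives one value, 3, under "PRA Block Size". It mentions no varying sizes, and nothing withholds the size from the site. PRA is not defined, and the algorithm of the sponsor's encoded B&A program is not described.
- **Arms and strata.** Under B&A Program in section 10, "subjects will be randomly assigned to one of the three treatment groups (up to 50 per group", for 150 in total. "The subjects will be stratified based on DMI Severity Score and age". The printed cut-offs are "Mild (2-5), Moderate (6-8), Severe (9-12); <=54, >54", which makes 3 × 2 = 6 strata.
- **Households.** "Subjects residing in the same household will be assigned to the same treatment group".
- **The water arm.** Section 7 lists plain water as this arm's product. The Water Control Group text in section 8 says "Subjects will rinse with 15ml of water for 30 seconds".
- **Order of events at Visit 2.** Section 3, Baseline/Day 1, opens with "Continuance criteria will be assessed". Random assignment follows, then kit distribution with a review of the written instructions.
- **Discretion.** Section 6 begins "Subjects may be excluded from the study or the analysis if they" and lists five criteria. One of them, a new condition or medication, is left to the judgement of the investigator or designee.
- **Masking.** Section 9 describes identically sized, coded kit boxes and a sealed code breaker. It says nothing about masking the contents or the instructions.

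**The concern.** When block size equals the number of arms, the end of each block can be worked out from its beginning. Someone who can tell only water from rinse knows that the rest of a block is rinse once water has appeared. After two rinses, the same person knows that the next subject gets water. The site collects DMI and age and holds the cut-offs, so following the sequence by stratum is feasible.

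The timing matters because continuance is assessed before assignment at Visit 2. A forecast could therefore exist while a subject can still be kept or excluded. Water against rinse is the contrast in all three hypotheses of section 14, and Hypothesis 1 is the gate to the other two. The primary endpoint is a subjective 5-point rating. Any selective entry that made the water arm differ at baseline would bear on every confirmatory test.

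**Working it through.** **The plan's own figures.** The documents state no predictability figure. Their one computed design figure, in section 11, reproduces. With a difference of 0.66, SD 1.1 and one-sided 0.025, the normal approximation gives 44 per group for 80% power. At the stated 45, power is 81.2% (normal) or 80.4% (t), and 45/0.9 = 50 per group. The check below therefore uses 150 subjects.

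**Assumptions for predictability.**
1. The entry in section 10 means permuted blocks of 3 within each stratum, one of each arm.
2. Staff recognise water, but cannot tell one rinse from the other, before the next subject in that stratum is assigned.
3. Staff track assignments by stratum.
4. The household rule is ignored.

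**Certain in advance, complete blocks of 3.**
- Position 1: never known, 0.
- Position 2: known (rinse) only if position 1 was water, 1/3.
- Position 3: always known, 1.
- Mean: (0 + 1/3 + 1)/3 = 4/9 = 44.4%, or 150 × 4/9 ≈ 67 subjects.

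**What is known.** Position 3 is water with probability 1/3, so known water is (1/3)/3 = 1/9 of assignments (about 17 of 150). Known rinse is 4/9 − 1/9 = 3/9 (about 50 of 150).

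**Incomplete last blocks.** A stratum of 25 has 8 full blocks and one extra subject: 8 × (4/3)/25 = 42.7%. Simulating 150 subjects over 6 strata gives a mean of about 43.1%, range 42.2% to 44.4%.

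**If recognition lags one subject within the stratum.** Only position 3 can be known, and only when position 1 was water: (0 + 0 + 1/3)/3 = 1/9 = 11.1%.

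**Best-guess accuracy, blocks of 3.**
- Position 1: guess rinse, 2/3.
- Position 2: (1/3 × 1) + (2/3 × 1/2) = 2/3.
- Position 3: 1.
- Mean: (2/3 + 2/3 + 1)/3 = 7/9 = 77.8%.

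Always guessing rinse is right for 2/3 = 66.7%, so the gain is 11.1 points.

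**Alternatives under the same assumptions.**

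| Scheme | Certain in advance | Best guess correct |
|---|---|---|
| Fixed 3 (current) | 4/9 = 44.4% | 7/9 = 77.8% |
| Fixed 6 | 13/45 = 28.9% | 67/90 = 74.4% |
| Random mix of 3 and 6 | about 9.6% | about 75% |

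The fixed-block rows are exact enumerations. The mixed row is a simulation with strata of 24, the two sizes equally likely, and an observer who knows both sizes but not their order and updates optimally after each assignment.

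**The case against.** The strongest case against is that 44% exaggerates the usable knowledge. Three quarters of it is only the knowledge that a subject will not get water, which is true of two thirds of subjects anyway. On best-guess accuracy, the current scheme gains 11 points over a constant guess. The mixed scheme removes only 2 to 3 of those points and does no better than fixed blocks of 6. This stands. The case for change rests on certain foreknowledge, which is the firmest basis for a deliberate decision about a subject.

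Several limits on the harm also stand. Eligibility is settled at Visit 1. Of the five continuance criteria, one applies to Day 8 only, three are factual, and only one rests on judgement, although the word *may* leaves some latitude on all of them. Stratification means that selection on DMI class or age group cannot readily unbalance the arms. Section 15 allows DMI or baseline moisture or dryness as covariates, but only as an option, so this is not a dependable safeguard.

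The mechanism also depends on details that are not shown. The B&A algorithm is not described. The household rule fixes a later cohabitant's arm outright and may break the block pattern.

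A reader might infer that assignment is simply unconcealed from those who decide who proceeds. The documents do not support that: they do not say whether the staff who review instructions also decide continuance. Nor do they describe visit scheduling, so re-ordering of subjects is conjecture. Nothing suggests that anyone would act on a forecast.

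Finally, block size does not cure the recognisable water arm, which is the root of the problem. That is true, but block size determines how far recognition of past assignments reveals future ones.

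**Conclusion.** The point holds as an inexpensive improvement to the randomisation, not as a demonstrated bias. With a fixed block of 3, water or rinse may be known for certain in advance for about 43-44% of assignments if recognition is prompt and strata are tracked, and for about 11% if recognition lags by one subject.

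These figures rest on the permuted-block reading of an undefined term, on staff recognising water when instructions are reviewed, and on leaving the household rule aside. They measure predictability. They should not be read as the size of a treatment-effect bias, which the documents give no means of estimating. Confidence is medium.

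**What to change.** In section 10, replace the single block size with a statement that block sizes vary at random within each stratum. Move the sizes themselves (3 and 6) out of the protocol that the site holds and into the sponsor's B&A specification. If the program does not use permuted blocks, state in section 10 what it does.

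Under the assumptions above, certain foreknowledge falls from about 44% to about 10%. Best-guess accuracy falls only from 77.8% to about 75%.

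The cost is one program setting and one protocol line. The downside is a slightly larger possible imbalance at the end of a stratum when a last block of 6 is incomplete, which is minor at an average of 150/6 = 25 subjects per stratum.

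Requiring the continuance decision to be recorded before the program is opened for a subject would not help. The forecast comes from earlier assignments in the stratum, and section 3 already places continuance before assignment.
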